1.3.2 Secondary Objectives

To estimate the incidence and characterize the outcome of all high grade (CTCAE v4.0 Grade 3-4 and Grade 5) select adverse events in subjects with advanced or metastatic NSCLC who have progressed during or after at least one prior systemic therapy and are treated with nivolumab monotherapy.

1.3.3 Exploratory Objective(s):

- To assess safety and tolerability of nivolumab, as measured by incidence and severity of AEs and specific laboratory abnormalities in all treated subjects, by tumor histology (SQ or NSQ), by subject subgroups, and in Cohorts A and B
- To estimate efficacy of nivolumab by measuring overall survival (OS), progression-free survival (PFS), objective response rate (ORR) based on investigator assessment, and duration of response (DOR) in all treated subjects, by tumor histology (SQ or NSQ), by subject subgroups, and in Cohorts A and B (OS, PFS and DOR only)
- To explore the evolution of Patient Reported Outcomes (PRO) using the Lung Cancer Symptoms Scale (LCSS) and EQ-5D instruments in all treated subjects, by subject subgroups, and in Cohorts A and B

- To estimate the proportion of subjects exhibiting disease-related symptom improvement by 12 weeks as measured by LCSS

- [REDACTED]
- [REDACTED]
- [REDACTED]

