4.3.5 Treatment Discontinuation Criteria

Tumor assessments for all subjects should continue as per protocol even if dosing is discontinued.

- Nivolumab treatment should be permanently discontinued for the following:
 - Any Grade 2 drug-related uveitis, eye pain or blurred vision that does not respond to topical therapy and does not improve to Grade 1 severity within the retreatment period OR requires systemic treatment
 - Any Grade 3 non-skin, drug-related adverse event lasting > 7 days, with the following exceptions:
 - ◆ Grade 3 drug-related uveitis, pneumonitis, bronchospasm, hypersensitivity reaction, or infusion reaction of any duration requires discontinuation
 - ◆ Grade 3 drug-related endocrinopathies, adequately controlled with only physiologic hormone replacement do not require discontinuation. Adrenal insufficiency requires discontinuation regardless of control with hormone replacement.
 - ◆ Grade 3 drug-related laboratory abnormalities do not require treatment discontinuation except:
 - Grade 3 drug-related thrombocytopenia > 7 days or associated with bleeding requires discontinuation
 - Grade ≥ 3 drug-related AST, ALT or total bilirubin requires discontinuation*
 - Concurrent AST or ALT > 3x ULN and total bilirubin > 2x ULN

* In most cases of Grade 3 AST or ALT elevation, study treatment will be permanently discontinued. If the investigator determines a possible favorable benefit/risk ratio that warrants

continuation of study treatment, a discussion between the investigator and the BMS Medical Monitor/designee must occur.

- Any Grade 4 drug-related adverse event or laboratory abnormality, except for the following events:
 - ◆ Grade 4 neutropenia \leq 7 days does not require discontinuation
 - ◆ Grade 4 lymphopenia or leukopenia does not require discontinuation
 - ◆ Isolated Grade 4 electrolyte imbalances/abnormalities that are not associated with clinical sequelae and are corrected with supplementation/appropriate management within 72 hours of their onset do not require discontinuation
 - ◆ Isolated Grade 4 amylase or lipase abnormalities those are not associated with symptoms or clinical manifestations of pancreatitis. The Sponsor Medical Monitor designee should be consulted for Grade 4 amylase or lipase abnormalities.
- Any dosing interruption lasting $>$ 6 weeks with the following exceptions:

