Radiographic tumor assessments will be conducted at Week 9 (\pm 5 days) and every 8 weeks (\pm 5 days) thereafter through 24 months of treatment, disease progression (or until discontinuation of study therapy in patients receiving nivolumab beyond progression), lost to follow-up, or withdrawal of study consent. After 24 months of treatment, tumor assessments will take place regularly every 12 weeks (\pm 5 days) until the end of treatment, disease progression (or

[figure not shown]
until discontinuation of study therapy in patients receiving nivolumab beyond progression), lost to follow-up, or withdrawal of study consent. Tumor assessments for all subjects should continue as per protocol even if dosing is interrupted. Tumor measurements should be made by the same investigator or radiologist for each assessment whenever possible. Changes in tumor measurements and tumor responses to guide ongoing study treatment decisions will be assessed by the investigator using RECIST 1.1 (see [Appendix 1](#) for details of RECIST 1.1).

[figure not shown]

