8.2 Populations for Analyses

- All enrolled subjects: all subjects who signed an informed consent form and were registered into the IVRS.
- All treated subjects: all subjects who received any nivolumab. This is the primary population for safety and efficacy analyses. Subpopulation analyses will be conducted by

tumor histology (SQ or NSQ), by subject subgroups (subgroup 1 to 4), and for Cohorts A and B.

- All randomized subjects: all subjects who were randomized to Cohort A or B after completing 1 year of treatment.
- All response evaluable subjects: all treated subjects who have baseline and at least one on-study evaluable tumor measurement.
- [REDACTED]
- [REDACTED]

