8.3.3 Exploratory Endpoint(s)

Safety and tolerability will be measured by the incidence of all adverse events, serious adverse events, deaths and laboratory abnormalities. Adverse event assessments and laboratory tests will be performed at baseline, and continuously throughout the study at the beginning of each subsequent cycle.

Efficacy data will be assessed by measuring OS, DOR, ORR and PFS. These endpoints are defined as follows:

- OS is defined as the time from first dosing date to the date of death. A subject who has not died will be censored at last known date alive. OS will be followed continuously while subjects are on the treatment and every 3 months via in-person or phone contact after subjects discontinue the study drug.
- DOR is defined as the time from first confirmed response (CR or PR) to the date of the initial objectively documented tumor progression as determined using RECIST 1.1 criteria or death due to any cause, whichever occurs first. For subjects who neither progress nor die, the DOR will be censored on the date of their last evaluable tumor assessment. DOR will only be evaluated in subjects with objective response of CR or PR.
- Objective response rate (ORR) is defined as the number and percentage of subjects with a best overall response (BOR) of confirmed complete response (CR) or partial response (PR).

Best overall response (BOR) is defined as the best response designation, recorded between the date of first dose and the date of the initial objectively documented tumor progression per RECIST v1.1 or the date of subsequent therapy, whichever occurs first. For subjects without documented progression or subsequent therapy, all available response designations will contribute to the BOR determination.

- Progression-free survival (PFS) is defined as the time from first dosing date to the date of the first documented tumor progression, as determined by investigators (per RECIST v1.1), or death due to any cause, whichever occurs first. Subjects who die without a reported prior progression will be considered to have progressed on the date of their death. Subjects who did not progress or die will be censored on the date of their last evaluable tumor assessment. Subjects who did not have any on study tumor assessments and did not die will be censored on the first dosing date.

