Descriptive statistics of safety (AE and lab data) including incidence, median values using the Kaplan-Meier (KM) product-limit method with 95% CI using Brookmeyer and Crowley method of time to onset and time to resolution, and rate of discontinuation due to event occurrence will be presented for all treated subjects, by tumor histology (SQ or NSQ), by subject subgroups, and all randomized subjects for Cohorts A and B. Time to onset is calculated from first dosing date to the event onset date. If a subject never experienced the given AE, the subject will be censored at the last contact date. Time to resolution is calculated from the AE onset date to AE end date. If an AE is ongoing at the time of analysis, the time to resolution will be censored at the last contact date.

8.4.4.2 *Efficacy Analyses*

[figure not shown]
OS and PFS will be summarized by KM product-limit method for all treated subjects and all response evaluable subjects, respectively. Median values of OS and PFS, along with two-sided 95% CI using Brookmeyer and Crowley method, will be calculated. Survival rates at 6, 12, 18 and 24 months will also be estimated using KM estimates on the OS curve for all treated subjects. Associated two-sided 95% CIs will be calculated using the Greenwood formula. This analysis will be performed for all treated subjects or for all response evaluable subjects for PFS. This analysis will also be performed by tumor histology (SQ or NSQ), by subject subgroups, and all randomized subjects for Cohorts A and B.

The ORR will be summarized by binomial response rates and their corresponding two-sided 95% exact CIs using the Clopper-Pearson method. This analysis will be performed for all response evaluable subjects. This analysis will also be performed by tumor histology (SQ or NSQ), by subject subgroups, and all randomized subjects for Cohorts A and B.

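### Section 8.4.4.2 analyses PFS and ORR in response-evaluable subjects only, although the objective and Section 8.2 specify all treated subjects; this inflates ORR and is expected to raise the PFS curve

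*Combined protocol and SAP*

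**What the plan says.** - **Objective.** Section 1.3.3, like the synopsis, sets out to estimate OS, "progression-free survival (PFS), objective response rate (ORR) based on investigator assessment, and duration of response (DOR) in all treated subjects".
- **Populations.** Section 8.2 says of all treated subjects: "This is the primary population for safety and efficacy analyses". It defines the narrower set as "All response evaluable subjects: all treated subjects who have baseline and at least one on-study evaluable tumor measurement".
- **PFS analysis.** Section 8.4.4.2 states: "OS and PFS will be summarized by KM product-limit method for all treated subjects and all response evaluable subjects, respectively". The same paragraph assigns PFS to the evaluable set a second time.
- **ORR analysis.** The next paragraph of Section 8.4.4.2 says: "This analysis will be performed for all response evaluable subjects". Both analyses are repeated by histology, by subgroup and for randomized Cohorts A and B.
- **PFS definition.** Section 8.3.3 counts death without prior progression as an event on the date of death, and adds: "Subjects who did not have any on study tumor assessments and did not die will be censored on the first dosing date".
- **Scan schedule.** Section 5.4.1: "Radiographic tumor assessments will be conducted at Week 9". Section 4.3.5: "Tumor assessments for all subjects should continue as per protocol even if dosing is discontinued".

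Section 8.4.4.2 offers no all-treated PFS or ORR analysis and gives no reason for the change of population.

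**The concern.** Whether a subject enters the response-evaluable set depends on what happens after the first dose: the subject must live and stay in the study long enough to be measured. Those who fail to do so are mostly early deaths, withdrawals and losses. Stopping treatment does not by itself exclude anyone, because scans continue.

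For ORR, excluding these subjects can only raise the estimate. For PFS, it deletes the earliest deaths, which are the events that pull the curve down first. The Section 8.3.3 censoring rule for unassessed subjects can never apply in a set that requires an assessment, so the PFS definition appears to have been written for all treated subjects.

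Two uses of the results are at stake. OS and PFS would be reported side by side on different subjects, and Section 8.5 foresees data cuts for publication. Section 1.1.2 also wants an efficacy signal in subgroup 4 (PS 2). If frailer subjects miss the first scan more often, their figures are inflated most.

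**Working it through.** **Inputs from the protocol.** 1280 treated (Section 3.1). Phase 1 ORR of 24% at 3 mg/kg, and 24-week PFS rates of 25% to 45% (Section 1.4.3.3). Historical second-line median OS of 6.7 to 8.3 months, or 10+ months in one trial (Section 1.4.2). First scan at Week 9, after 8 weeks.

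**Assumption.** The excluded share f is not stated. I use 5% to 20%.

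**Plan's own figures.** The plan gives no ORR or PFS figure for this trial. Its exact confidence intervals in Table 8.1-1 reproduce in all 16 rows (for example 4/780 gives 0.14% to 1.31%) and are not in dispute.

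**Is 5% to 20% plausible?** With exponential survival, the share dead by 8 weeks is 1 − exp(−ln 2 × (8/4.345)/median OS in months):
- 6.7 months: 17.3%
- 8.3 months: 14.3%
- 10 months: 12.0%

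**ORR.** A confirmed responder has been measured on study, so the numerator is fixed and ORR(evaluable) = ORR(treated)/(1 − f).

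**PFS after the first scan.** If a share e dies before any scan and is dropped, S(evaluable) = S(treated)/(1 − e). Living unscanned subjects are censored on the first dosing date, so losing them is neutral. The PFS columns below assume that every excluded subject is an early death (e = f).

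| Excluded | ORR 24% reads | 24-week PFS 25% reads | 24-week PFS 45% reads |
|---|---|---|---|
| 5% | 25.3% | 26.3% | 47.4% |
| 10% | 26.7% | 27.8% | 50.0% |
| 12.0% | 27.3% | 28.4% | 51.1% |
| 17.3% | 29.0% | 30.2% | 54.4% |
| 20% | 30.0% | 31.3% | 56.3% |

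**Against sampling error.** The 95% half-width for an ORR of 24% is 1.96 × √(0.24 × 0.76/1280) = 2.34 points. The bias exceeds it when f > 1 − 24/26.34 = 8.9%. In whole subjects at f = 20%, 307/1280 = 24.0% (exact 95% CI 21.7 to 26.4) becomes 307/1024 = 30.0% (27.2 to 32.9), and the intervals do not overlap.

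**Between subgroups.** With an assumed 5% excluded in one subgroup and 20% in another, the same true ORR of 24% reads as 25.3% and 30.0%.

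**Median PFS.** I simulated 2,000,000 subjects per case with exponential death and latent progression, progression read at the next 8-weekly scan, and all deaths before the first scan excluded. OS medians were 6.7, 8.3 and 10 months.
- Underlying median PFS 2.6 months: 3.68 months in both sets, so no shift.
- Underlying median PFS 3.2 months: 3.68 months becomes 4.51, 4.25 and 4.02 months respectively.

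A simpler exponential model without a scan grid, with 5% to 20% early deaths dropped, moves the median from 12.0 to 12.9–15.9 weeks, or from 20.8 to 22.4–27.6 weeks.

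**The case against.** - **Section 8.2 already settles it.** It names all treated subjects as primary, so this could be read as an inconsistency rather than a deliberate choice. That is fair. But Section 8.4.4.2 is the section that specifies the analyses, and it names the evaluable set for PFS twice and for ORR once. Followed as written, it gives the biased figures.
- **The PFS sizes are soft.** This stands. Section 8.4.4.2 plans landmark rates for OS only, so the 24-week PFS rates show how far the curve moves and are not planned outputs. The median shift depends on where the true median falls relative to the scan at 16 weeks (3.68 months), and can be nil. The 56.3% figure is not credible: a 24-week PFS of 45% implies only 1 − 0.45^(1/3) = 23% with any event by week 8 under an exponential curve, leaving almost no room for progression beside 20% deaths.
- **The PFS rise is expected, not certain.** A late death with no scan at all could pull the other way, and an unscheduled scan before Week 9 could keep an early death in the set. The ORR rise is certain whenever anyone is excluded.
- **Sampling error dominates in small subgroups.** Subgroup 4 is limited to 100 subjects (Section 1.1.1). There the half-width is 1.96 × √(0.24 × 0.76/100) = 8.4 points, more than the 6-point bias at f = 20%. That limits what the subgroup can show, but does not remove a bias of known direction.
- **The endpoints are exploratory and untested.** True, and this limits the consequence. It does not justify a population that contradicts the objective.

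**Conclusion.** The concern holds. Section 8.4.4.2 contradicts the objective and Section 8.2 on the population for PFS and ORR, and its choice favours the drug. ORR is inflated by 1/(1 − f): about 1 to 6 points on 24% if 5% to 20% are excluded, which is an assumed range. PFS is expected to be raised through the loss of early deaths, by an amount the documents cannot fix; the median may not move.

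OS and the primary and secondary safety analyses are untouched. In Cohorts A and B the effect is negligible, because those subjects have already completed about 52 weeks of treatment. For DOR the mismatch is one of wording only, since responders are evaluable by definition. The point should be fixed, but it does not threaten the trial's main purpose.

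**What to change.** Revise Section 8.4.4.2 as follows:

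1. Make all treated subjects the population for PFS and ORR, overall, by histology and by subgroup.
2. For ORR, count subjects without an on-study assessment as non-responders. For PFS, apply the Section 8.3.3 event and censoring rules as they stand.
3. Keep the response-evaluable analysis as a labelled supportive analysis.
4. Report the number excluded from that set and the reason (death, withdrawal, lost to follow-up, not scanned), overall and by subgroup.
5. Reword the DOR population as all treated subjects with a confirmed CR or PR. No DOR number changes.

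The cost is a protocol/SAP text revision, with no extra data or visits. The PFS and ORR figures are likely to be less favourable.

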Study Design: In this safety study of nivolumab monotherapy, subjects will undergo screening evaluations to determine eligibility within 28 days prior to first dose. Eligible subjects will be treated with nivolumab administered intravenously over 30 minutes at 3 mg/kg every two weeks. Each 14 day dosing period will constitute a cycle. After 1 year (52 weeks) of treatment all subjects who are still on treatment will be randomized (1:1) to one of the two cohorts, Cohort A or Cohort B.

- Cohort A: Subjects randomized to Cohort A will continue to receive treatment until disease progression, unacceptable toxicity, or withdrawal of informed consent.
- Cohort B: Subjects randomized to Cohort B will discontinue treatment at 1 year (52 weeks). After randomization, subjects will remain on the study and will follow all study assessments [REDACTED] Upon progression, subjects can receive retreatment. If subjects are [REDACTED]

[REDACTED] Subjects who are retreated can continue to receive study drug until further progression, unacceptable toxicity, or withdrawal of informed consent.

Study treatment can continue beyond initial investigator assessed progression, as specified in criteria presented in [Section 4.3.4 Treatment Beyond Disease Progression](#).

The study will enroll subjects into 4 subgroups as detailed in [Table 3.1-1](#). Enrollment will open first to subgroup 1 only. A decision to open enrollment for each of the other subgroups 2-4 will be dependent upon the sponsor review of data from the ongoing Phase 2 and 3 studies for each patient population. The decision will take into account the overall risk/benefit profile for each patient population and the determination will be made whether or not to collect additional safety and efficacy data to supplement that already collected.

At the time of Protocol Amendment 01 (June 2014), all subgroups were opened.

Protocol Amendment 03 (November 2014) allowed for continued enrollment beyond 780 subjects in two of the study subgroups. However, as of Protocol Amendment 04 (December 2014), enrollment under Amendment 03 will stop, but enrollment will continue until 500 additional subjects are treated. Enrollment will continue until a total of 1280 subjects are treated.

[REDACTED]

Under Protocol Amendment 04, all subjects will receive nivolumab by IV infusion administered over 30 minutes, including new and existing subjects enrolled in the study and subjects enrolled under Amendment 02.

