1.1.2.1 *Rationale for Exploring Fixed Treatment Duration vs Continuous Treatment on Maintaining Tumor Response*

In the current Phase 2/3 trials subjects are continuously treated with nivolumab on a schedule of 3 mg/kg IV every 2 weeks until disease progression or unacceptable toxicity or withdrawal of informed consent. Safety and efficacy profile of nivolumab monotherapy in a schedule with defined treatment duration and retreatment upon disease progression has not been previously assessed. There is evidence for other cancer immunotherapies that administration of treatment for a fixed period of time can translate into prolonged benefit, eg, ipilimumab or aldesleukin.^{10,11,12,13,14,15} In subjects with NSCLC treated in MDX1106-03, 50% of the observed responses occurred rapidly and were demonstrated at first tumor assessment (at 8 weeks). The most delayed response was observed shortly after 30 weeks.¹⁶ After 1 year of treatment, 27% of NSCLC subjects (10 of 37 total; 5 of 18 for SQ and 5 of 19 for NSQ) treated at 3 mg/kg dose level were still on treatment. Moreover, most of them (9 of 10) continued to experience durable responses. For those patients that do progress after treatment discontinuation, will be allowed to receive retreatment until progression, unacceptable toxicity, or withdrawal of informed consent. Response to retreatment with immunotherapies such as ipilimumab has been shown.¹⁷ Hence, the intention to obtain information on the effect of different treatment durations on maintaining the tumor response is warranted, as it may inform on the value of further testing of alternative schedules.

1.1.3 *Rationale for Nivolumab Monotherapy*

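### Cohorts A and B are randomised at week 52 but only summarised one by one, with OS and PFS timed from first dose; the visible plan contains no between-cohort estimate.

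*Combined protocol and SAP*

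**What the plan says.** The synopsis and section 3.1 set the design: "After 1 year (52 weeks) of treatment all subjects who are still on treatment will be randomized (1:1) to one of the two cohorts". Those assigned to Cohort A continue; those assigned to Cohort B stop and may be retreated on progression. Section 1.1.2.1 gives the reason: "the intention to obtain information on the effect of different treatment durations on maintaining the tumor response is warranted". Section 1.1.1 puts the aim more modestly, as an exploratory description of two treatment durations. Section 8.1.1 gives an expected number randomised, but no hypothesis, power or event target.

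Section 8.3.3 sets the time origins: "OS is defined as the time from first dosing date to the date of death"; "Progression-free survival (PFS) is defined as the time from first dosing date to the date of the first documented tumor progression"; and "DOR is defined as the time from first confirmed response (CR or PR) to the date of the initial objectively documented tumor progression".

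Section 8.4.4.2 plans one-sample summaries. For medians: "Median values of OS and PFS, along with two-sided 95% CI using Brookmeyer and Crowley method, will be calculated". For fixed times: "Survival rates at 6, 12, 18 and 24 months will also be estimated using KM estimates on the OS curve for all treated subjects", with Greenwood intervals. ORR gets exact intervals. DOR gets medians and the percentage still in response at 3 to 24 months and at study end. The cohorts enter through a repeated sentence: "This analysis will also be performed by tumor histology (SQ or NSQ), by subject subgroups, and all randomized subjects for Cohorts A and B". AE summaries (sections 8.4.3 and 8.4.4.1) and PRO summaries (section 8.4.4.3) are repeated by cohort in the same way.

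**The concern.** Subjects are randomised so that the effect of stopping can be learned. The analysis then treats the randomised cohorts as one more grouping variable, beside histology and the enrolment subgroups. No endpoint is timed from randomisation, and no quantity compares B with A.

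A reader of the report would get two sets of curves and intervals and would have to build the comparison. For PFS only medians are planned, and these may not be reached. The study is open-label (section 4.4), and section 8.5 allows repeated data cuts for publication. With no contrast fixed in advance, the time origin, population and effect measure can all be chosen after the data are seen.

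**Working it through.** **1. Inputs.** 10 of 37 subjects, interval 12.7% to 41.3%, and 99 to 322 randomised (section 8.1.1); 780 treated (section 8.1) and 1280 treated (section 3.1); randomisation at 52 ± 2 weeks (section 4.2). The documents give no event rate or hazard ratio for B versus A, so those used below are assumptions.

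**2. The plan's own figure.** p = 10/37 = 0.270. The Wald interval, p ± 1.96·√(p(1−p)/37), is 12.7% to 41.3%. Then 780 × 0.127 = 99 and 780 × 0.413 = 322, so the stated range reproduces. Scaled to 1280: 1280 × 0.127 = 163 and 1280 × 0.413 = 529.

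**3. What the per-cohort outputs can show.**
- OS at 6 and 12 months: every randomised subject was alive at about 52 weeks, so both rates are essentially 100% in both cohorts. Only the ± 2 week window leaves room for a death just before month 12.
- OS at 18 and 24 months: these lie about 6 and 12 months after randomisation. Section 3.2 puts follow-up at 4 years from randomisation.
- LCSS improvement at week 12: 52 − 12 = 40 weeks before randomisation, so assignment cannot affect it.
- DOR percentages: in MDX1106-03 half the responses were seen at 8 weeks and the latest shortly after 30 weeks (section 1.1.2.1). On that timing the 3-month point falls no later than about week 30 + 13 = 43. The 6-month point falls by week 52 for any response up to week 26.

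**4. Dilution of medians.** Suppose post-randomisation medians of 24 and 12 months, a ratio of 2.0. From first dose they read 36 and 24, a ratio of 1.5. With 12 and 6 months, they read 24 and 18, a ratio of 1.33.

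**5. Does the origin bias an OS contrast?** No. Adding the same 12 months to everyone leaves the order of events unchanged. A simulated Cox hazard ratio was 2.206 with either origin, and 2.211 when randomisation varied by ± 2 weeks.

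**6. What a reader could derive.** With assumed exponential post-randomisation medians of 24 and 12 months, the 24-month OS rates are 0.5^(12/24) = 70.7% and 0.5^(12/12) = 50.0%, a difference of 20.7 points. Without censoring, the 95% half-width is 1.96·√(0.707·0.293/n + 0.5·0.5/n) with n per cohort: ± 18.8 points for 99 randomised and ± 10.4 for 322. An indirect OS contrast is therefore possible.

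**7. PFS before randomisation.** Section 4.3.4 permits treatment beyond RECIST progression. The synopsis and section 3.1 randomise everyone still on treatment, while sections 4.1, 4.2 and 8.1.1 speak of subjects still benefiting. Section 8.1.1 describes the 10 of 37 as progression-free at 48 weeks; the synopsis describes them as still on treatment. None of these clearly keeps out a subject who has already progressed. Such a subject's PFS event, dated before randomisation, would count in the cohort curve.

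**8. Precision of the missing estimate.** At 1:1, SE(log HR) = 2/√d for d events, and the interval at HR = 1 is exp(± 1.96·2/√d). The event fractions of 40% and 80% are assumed.

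| Randomised | d at 40% | 95% CI | d at 80% | 95% CI |
|---|---|---|---|---|
| 99 | 40 | 0.54–1.86 | 79 | 0.64–1.55 |
| 322 | 129 | 0.71–1.41 | 258 | 0.78–1.28 |
| 163 | 65 | 0.61–1.63 | 130 | 0.71–1.41 |
| 529 | 212 | 0.76–1.31 | 423 | 0.83–1.21 |

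**The case against.** The strongest reply is that the plan does what it promises. The duration part is exploratory, is meant to describe, and carries no hypothesis. The plan gives more than medians by cohort, and the later OS rates with their intervals let a reader form a difference. DOR, the endpoint nearest to maintaining response, runs from response and not from first dose. The data will also remain available for a hazard ratio. All of this stands, and it rules out several stronger readings that a reader might draw:

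- *The duration question goes unanswered, or the randomisation is wasted.* The per-cohort summaries fit the stated descriptive aim, and randomisation still makes the cohorts comparable.
- *Timing from first dose biases the comparison.* For OS it does not (step 5). It makes some outputs uninformative and dilutes others.
- *This would be a bias-free comparison.* Treatment is open-label, progression is investigator-assessed, and Cohort B may be retreated, so OS compares strategies that include retreatment.
- *A powered test was needed.* Nothing in the objectives calls for one.

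Parts of the exploratory objectives and analysis populations are redacted, so the absence of a contrast is established only for the visible text.

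The reply does not supply the estimate. A hazard ratio or rate difference with its interval is itself descriptive and needs no test. A contrast that readers assemble themselves is not pre-specified. Fixed-time rates are planned for OS but not for PFS, so no PFS rate difference can be formed from the planned output.

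**Conclusion.** The point holds as a gap in an exploratory analysis: the effect of stopping at one year is described but not estimated. Two of the four planned OS rates carry essentially no information on A versus B, and the other two reach at most about 12 months of a possible 4 years after randomisation. PFS has the further defect that events before randomisation may be counted; how many is unknown.

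The missing hazard ratio would have a 95% CI at HR = 1 between 0.54–1.86 (99 randomised, 40% with events) and 0.83–1.21 (529 randomised, 80% with events). That range rests on the assumed event fractions and on the MDX1106-03 proportion carrying over to this trial. At the low end the estimate would be imprecise, but the interval would show this openly, which two separate medians do not. The change is worth making, but neither the primary nor the secondary safety objective depends on it.

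**What to change.** In section 8.3.3, add OS and PFS timed from the randomisation date, for all randomised subjects. For PFS, analyse those without RECIST progression before randomisation and report by cohort how many are excluded. The exclusion uses only pre-randomisation information, so the comparison stays randomised.

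In section 8.4.4.2, add the Cohort B versus A hazard ratio for OS and PFS. Also add differences in Kaplan-Meier rates at fixed times after randomisation (for example 6, 12 and 24 months), each with a 95% CI. For the response question in section 1.1.2.1, add the between-cohort hazard ratio for loss of response in subjects in response at randomisation. Label all of this exploratory, with no hypothesis test. The first-dose summaries can stay for all treated subjects.

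Reconcile the wording on who is randomised (still on treatment, or still benefiting), and restate the expected number randomised for 1280 treated.

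The cost is analysis wording and one table, with no new data collection if progression and randomisation dates are recorded as the schedule implies. The drawback is that the estimates may be imprecise and could be over-read, so the descriptive label must go with them.
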